4.4. Exclusion Criteria for Part A: Healthy Subjects

Subjects from Part A will be excluded from the study if they satisfy any of the following criteria at the Screening visit unless otherwise stated:

1. Significant history or clinical manifestation of any metabolic, allergic, dermatological, hepatic, renal, haematological, pulmonary, cardiovascular, gastrointestinal, neurological, respiratory, endocrine, or psychiatric disorder, as determined by the Investigator (or designee).
2. History of febrile illness within 7 days prior to the first dose of study drug or subjects with evidence of active infection.
3. History of significant hypersensitivity, intolerance, or allergy to any drug compound, food, or other substance, unless approved by the Investigator (or designee).
4. History of stomach or intestinal surgery or resection that would potentially alter absorption and/or excretion of orally administered drugs (uncomplicated appendectomy and hernia repair will be allowed, but not cholecystectomy).
5. Any of the following:
 - a. QTcF > 450 msec confirmed by repeat measurement.
 - b. QRS duration > 110 msec confirmed by repeat measurement.
 - c. PR interval > 220 msec confirmed by repeat measurement.
 - d. findings which would make QTc measurements difficult or QTc data uninterpretable.
 - e. history of additional risk factors for torsades de pointes (eg, heart failure, hypokalaemia, family history of long QT syndrome).
6. History of alcoholism or drug/chemical abuse within 1 year prior to Check-in.
7. Alcohol consumption of > 21 units per week for males and > 14 units per week for females. One unit of alcohol equals $\frac{1}{2}$ pint (285 mL) of beer or lager, 1 glass (125 mL) of wine, or $\frac{1}{6}$ gill (25 mL) of spirits.
8. Positive alcohol breath test result or positive urine drug screen (confirmed by repeat) at Screening or Check-in.

9. Positive hepatitis panel and/or positive human immunodeficiency virus (HIV) test ([Appendix 2](#)).
10. Participation in a clinical study involving administration of an investigational agent or vaccine (new chemical entity) or having received a biological product in the past 90 days prior to dosing.
11. Use or intend to use any medications/products known to alter drug absorption, metabolism, or elimination processes, including St. John's wort, within 30 days prior to dosing, unless deemed acceptable by the Investigator (or designee).

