4.5. Exclusion Criteria for Part B: Healthy Subjects

Subjects from Part B will be excluded from the study if they satisfy any of the following criteria at the Screening visit unless otherwise stated:

1. Significant history or clinical manifestation of any metabolic, allergic, dermatological, hepatic, renal, haematological, pulmonary, cardiovascular, gastrointestinal, neurological, respiratory, endocrine, or psychiatric disorder, as determined by the Investigator (or designee).

2. History of febrile illness within 7 days prior to the first dose of study drug or subjects with evidence of active infection.
3. History of significant hypersensitivity, intolerance, or allergy to any drug compound, food, or other substance, unless approved by the Investigator (or designee).
4. History of stomach or intestinal surgery or resection that would potentially alter absorption and/or excretion of orally administered drugs (uncomplicated appendectomy and hernia repair will be allowed, but not cholecystectomy).
5. Clinically significant ECG abnormalities or QTcF greater than 450 msec for males and 470 msec for females at either Screening or Day 1 predose, or any prior history of QT abnormality.
6. History of alcoholism or drug/chemical abuse within 1 year prior to Check-in.
7. Alcohol consumption of > 21 units per week for males and > 14 units per week for females. One unit of alcohol equals ½ pint (285 mL) of beer or lager, 1 glass (125 mL) of wine, or 1/6 gill (25 mL) of spirits.
8. Positive alcohol breath test result or positive urine drug screen (confirmed by repeat) at Screening or Check-in.
9. Positive hepatitis panel and/or positive HIV test ([Appendix 2](#)).
10. Participation in a clinical study involving administration of an investigational agent or vaccine (new chemical entity) or having received a biological product in the past 90 days prior to dosing.
11. Use or intend to use any medications/products known to alter drug absorption, metabolism, or elimination processes, including St. John's wort, within 30 days prior to dosing, unless deemed acceptable by the Investigator (or designee).
12. Use or intend to use any prescription medications/products other than hormone replacement therapy, oral, implantable, transdermal, injectable, or intrauterine contraceptives within 14 days prior to dosing, unless deemed acceptable by the Investigator (or designee).

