4.6. Exclusion Criteria for Part C: Subjects with Suspected NASH and Liver Fibrosis

Subjects from Part C will be excluded from the study if they satisfy any of the following criteria at the Screening visit unless otherwise stated:

1. If diabetic and diabetes is other than T2DM.
2. Subjects, who have had bariatric surgery of any kind or, in the opinion of the Investigator, have experienced a clinically significant change in body weight within the 3 months prior to Screening.
3. History of any known serious disease (such as cancer, except skin basocellular carcinomas, major infection, clinically significant gastrointestinal disorder, major autoimmune disease) or other disease which in the Investigator's opinion would exclude the patient from the study.
4. The following clinical laboratory results at Screening:
 - Total Bilirubin $> 2 \times$ ULN
 - ALT > 155 U/L for females and > 185 U/L for males
 - AST > 155 U/L for females and > 200 U/L for males
5. Other abnormal clinical laboratory values that are considered clinically significant for this population.
6. History of febrile illness within 7 days prior to the first dose of study drug or subjects with evidence of active infection.
7. History of significant hypersensitivity, intolerance, or allergy to any drug compound, food, or other substance, unless approved by the Investigator (or designee).
8. History of stomach or intestinal surgery or resection that would potentially alter absorption and/or excretion of orally administered drugs (uncomplicated appendectomy, cholecystectomy, and hernia repair will be allowed).
9. Clinically significant ECG abnormalities or QTcF greater than 450 msec for males and 470 msec for females at either Screening or Day 1 predose, or any prior history of QT abnormality.
10. History of alcoholism or drug/chemical abuse within 1 year prior to Check-in.
11. Alcohol consumption of > 14 units per week for males and for females. One unit of alcohol equals $\frac{1}{2}$ pint (285 mL) of beer or lager, 1 glass (125 mL) of wine, or $\frac{1}{6}$ gill (25 mL) of spirits.

12. Positive alcohol breath test result or positive urine drug screen (confirmed by repeat) at Screening or Check-in.
13. Positive hepatitis panel and/or positive HIV test ([Appendix 2](#)).
14. Clinically significant laboratory abnormalities, as determined by the Investigator.

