15. A creatinine clearance of less than 50 mL/min (as calculated by Cockcroft-Gault equation) or estimated glomerular filtration rate (eGFR) < 60 mL/[min*1.73 m²] at Screening.
16. Participation in a clinical study involving administration of an investigational agent or vaccine (new chemical entity) or having received a biological product in the past 90 days prior to dosing.
17. Use or intend to use any medications/products known to alter drug absorption, metabolism, or elimination processes, including St. John's wort, within 30 days prior to dosing, unless deemed acceptable by the Investigator (or designee).
18. Use or intend to use slow-release medications/products considered to still be active within 14 days prior to Check-in, unless deemed acceptable by the Investigator (or designee).
19. Subject taking any antidiabetic medications, with the exception of metformin, sulfonylureas, gliptins, and sodium/glucose co-transporter 2 inhibitors, within 3 months prior to Screening.
20. Use of any of the following non-permitted medication within 6 months prior to Screening: amiodarone, bile salt chelators, methotrexate, pharmacological doses of systemic corticosteroids for at least 2 consecutive weeks, or any other medications known to affect liver function.
21. Use or intend to use any nonprescription medications/products including vitamins (Vitamin E at dose <400 U is permitted, Vitamin E at dose 400 U is allowed if on a stable dose for 2 months prior), minerals, and phytotherapeutic/herbal/plant-derived preparations within 7 days prior to Check-in, unless deemed acceptable by the Investigator (or designee).
22. Receipt of blood products within 2 months prior to Check-in and donation of blood from 3 months prior to Screening, plasma from 2 weeks prior to Screening, or platelets from 6 weeks prior to Screening.
23. Poor peripheral venous access.
24. Have previously completed or withdrawn from this study investigating GB1211, and have previously received the investigational product.
25. Subject who, in the opinion of the Investigator (or designee), should not participate in this study.
26. Subject is not willing to minimise or avoid exposure to natural or artificial sunlight (tanning beds or UVA/B treatment) following administration of study drug until 24 hours after the last dose.

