6.1.2. Concomitant Therapies for Part C

Subjects of Part C will refrain from use of any prescription or nonprescription medications/products during the study with exceptions, as stated in [Section 4.6](#), until the Follow-up visit, unless the Investigator (or designee) and/or Sponsor have given their prior consent.

Paracetamol/acetaminophen (2 g/day for up to 3 consecutive days) and hormone replacement therapy are acceptable concomitant medications.

The administration of any other concomitant medications during the study is prohibited without prior approval of the Investigator (or designee), unless its use is deemed necessary for treatment of an AE. Any medication taken by a subject during the course of the study and the reason for its use will be documented in the source data.

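### Part A's torsades-risk exclusion is not carried into the Part C criteria, so a family history of long QT is left to Investigator discretion

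*Protocol*

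**What the plan says.** **Part A (Protocol 4.4, criterion 5).** Alongside the QTcF, QRS and PR limits, item 5e excludes "history of additional risk factors for torsades de pointes (eg, heart failure, hypokalaemia, family history of long QT syndrome".

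**Part B (4.5, criterion 5) and Part C (4.6, criterion 9).** The two share one wording. Part C's begins "Clinically significant ECG abnormalities or QTcF greater than 450 msec for males and 470 msec for females at either Screening or Day 1 predose". The Part B text continues "at either Screening or Day 1 predose, or any prior history of QT abnormality", and Part C ends the same way. Neither has an item on torsades risk factors.

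**General criteria in Part C (4.6).** Criterion 3 begins "History of any known serious disease (such as cancer, except skin basocellular carcinomas, major infection" and also allows exclusion for other disease on the Investigator's opinion. Criterion 5 covers other abnormal laboratory values judged clinically significant for this population. Criterion 14 reads "Clinically significant laboratory abnormalities, as determined by the Investigator", and criterion 25 reads "Subject who, in the opinion of the Investigator (or designee), should not participate in this study".

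**Drug rules in Part C.** Criteria 17 to 21 deal with pharmacokinetic interaction, slow-release products, antidiabetics, drugs acting on the liver, and nonprescription products. Criterion 20 bars amiodarone by name, in a list that closes with "or any other medications known to affect liver function". Section 6.1.2 opens with a default ban on prescription and nonprescription products, subject to the exceptions in 4.6 and to prior consent. It then says "The administration of any other concomitant medications during the study is prohibited without prior approval of the Investigator (or designee", with an exception for treating an adverse event. None of these rules mentions QT.

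**The concern.** The part with the most protective wording on arrhythmia risk is the one with the least exposure. Part A subjects are healthy, receive one or two doses, stay on site to 48 hours and have telemetry for the first 4 hours. Part C subjects have type 2 diabetes or metabolic syndrome and are dosed for 42 days, mostly at home, with no telemetry planned.

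The protocol gives its own reasons for caution. Section 1.3 reports hERG inhibition at every concentration in the GLP study. Section 1.4 reports QT and QTc increases in dogs; these were judged not adverse, and telemetered dogs showed no ECG findings.

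At stake is whether some people at raised inherited risk are kept out of Part C by a stated rule or only if an Investigator thinks to exclude them.

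**Working it through.** The plan states no figure on this point, so the check sets the criteria side by side. The arithmetic below is context only.

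| Risk factor | Part A | Part B | Part C |
|---|---|---|---|
| Heart failure | 5e, by name | Criterion 1, significant cardiovascular history | Criterion 3 (open list, cardiac disease not named) or 25 |
| Current hypokalaemia | 5e, by name | Inclusion 3, healthy on laboratory tests | Criteria 5 and 14, by judgement |
| Family history of long QT, own QTcF normal | 5e, by name | Criterion 19 only (Investigator's opinion) | Criterion 25 only (Investigator's opinion) |
| Prescription drugs at entry | Criterion 12 | Criterion 12 | No general exclusion; criteria 17 to 21 by class, then 6.1.2 |

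The third row is the clear gap. Criterion 9 acts on the subject's own ECG and own QT history, so it does not touch a relative's diagnosis. In the first two rows a route to exclusion exists in Part C, but it is less explicit than in Part A.

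**Exposure away from the site** (3.1.3, 5.2, Appendix 6 Table 3)
- Planned doses: 41 × 2 + 1 = 83.
- On site: two on Day 1, one on Day 2, one or two on Day 41, one on Day 42, so 5 to 6.
- At home: 83 − 6 = 77 (92.8%) to 83 − 5 = 78 (94.0%).
- Home period, Day 2 to Day 41: 39 days. The 12-lead ECG and clinical chemistry (which includes potassium) are each scheduled twice in it, on Days 14 and 28.

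**Relevance of the hERG finding** (1.3, 1.5, 3.7)
- IC50 = 5.06 µM = 2700 ng/mL, so 1 µM = 2700 / 5.06 = 533.6 ng/mL.
- Individual Cmax ceiling = 19755 ng/mL; human free fraction = 5.34%.
- Free concentration at the ceiling: 19755 × 0.0534 = 1055 ng/mL, or 1055 / 533.6 = 1.98 µM.
- Margin to the IC50: 2700 / 1055 = 2.6-fold. The GLP study reported 28.51% inhibition at 1 µM.

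This is an upper bound. It treats the assay concentration as free drug and assumes exposure at the ceiling, whereas the Part C dose is still to be determined. It shows that a QT-risk exclusion is relevant, not that a QT effect is expected.

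**Screen failures.** If a fraction p of otherwise eligible candidates were newly excluded, filling 25 places would need 25/(1 − p) − 25 more candidates. The documents give no p, so these values are assumed.

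| p (assumed) | Extra candidates |
|---|---|
| 2% | 0.5 |
| 5% | 1.3 |
| 10% | 2.8 |
| 20% | 6.3 |
| 30% | 10.7 |

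**The case against.** **Part A's criterion 5 may be specific to Part A.** That part has continuous 12-lead ECG recording with a view to a thorough-QT waiver (3.4). Parts B and C have their own rule, which adds clinically significant ECG abnormalities, prior QT abnormality and a Day 1 predose check. This explains the QRS, PR and measurability items (5b to 5d), and there is no case for copying those. It explains 5e less well, because arrhythmia risk does not end with Part A. The documents give no reason either way, so the omission cannot be called an oversight.

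**Part B is largely covered.** Criterion 1, criterion 12, inclusion 3 and continuous residence from Day -1 to Day 11 leave little beyond family history. This stands.

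**Concomitant drugs are already controlled.** A reader might infer that QT-prolonging drugs are freely allowed in Part C. The documents do not support that: 6.1.2 bans other medication by default and amiodarone is barred by name. What is missing is a stated QT standard for granting approval. Section 6.1.1 lacks one for Parts A and B too, so this is not an inconsistency between parts.

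**Other safeguards exist.** Part C starts only after review of Part A and at least one Part B cohort. The daily dose is capped by Part A experience, the study halts on related serious or repeated related severe events (3.7), individual dosing stops on QTcF (4.8), and telemetry may be added if Part A shows findings (7.3.4.2). These limit the risk, though the QTcF stop acts only after exposure and only when an ECG is taken. The continuous recordings are archived without analysis (7.3.4.3), so they do not inform the review before Part C.

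**The home-dosing figures describe the setting, not the size of the gap.** This also stands. Likewise, past and corrected hypokalaemia is covered by 5e's wording as a history and not named in Part C, but it is a thin residue and carries no weight here.

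**Conclusion.** The point holds in a limited form. Item 5e is absent from Part C criterion 9, and Part C lacks the two Part B criteria that would otherwise cover much of the same ground. The consequence is that one named risk factor, family history of long QT with a normal own QTcF, rests on Investigator discretion alone. Two others, heart failure and current hypokalaemia, rest on general or judgement-based criteria. In Part B the remaining gap is small and mainly family history.

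A reader might infer that Part C admits people with heart failure or low potassium. It does not follow: criteria 3, 5, 14 and 25 each allow exclusion.

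The number of affected candidates cannot be estimated from the documents. No sample size or analysis is involved. This is a cheap safety improvement, worth making because it replaces discretion with the protocol's own wording.

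**What to change.** **Main change.** Add the 5e wording to 4.6 criterion 9 and, for consistency, to 4.5 criterion 5. The SAP (section 7) already names Part B doses, so the Part B edit may matter only for any cohorts added under Protocol 3.3.

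**Optional change.** A rule on QT-prolonging drugs would be a new requirement, not a carry-over from Part A. If wanted, state it in 6.1.2 as a condition on approval: no concomitant drug with known torsades risk during dosing, except where needed to treat an adverse event, in which case study drug is stopped. The sponsor would need to name the reference list. The rule should not be an entry in criterion 20, where it would take on a 6-month look-back and exclude people for a short course finished months earlier.

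**Cost.** The main change is wording in two criteria. Medical history, 12-lead ECG, clinical chemistry and prior medication are already collected at Screening; family history needs at most one added question. The downside is slightly more screen failures: fewer than 3 extra candidates for 25 places if up to 10% were newly excluded, and more at higher rates, all of them assumed. Part C's dose and randomisation are still to be confirmed (3.5, 5.3), so the edit could go in with those details.

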4.7. Subject Number and Identification

Subjects will have a unique identification number used at Screening. Subjects will be assigned a subject number at the time of first dose/dosing. Assignment of subject numbers will be in ascending order and no numbers will be omitted (eg, in Part A Subjects 0101, 0102, etc, in Part B Subjects 0201, 0202, etc, in Part C Subjects 0301, 0302, etc). Replacement subjects (Section 4.8) will be assigned a subject number corresponding to the number of the subject he/she is replacing plus 1000 (eg, Subject 1101 replaces Subject 101).

Subjects will be identified by subject number only on all study documentation. A list identifying the subjects by subject number will be kept in the Site Master File.

4.8. Subject Withdrawal and Replacement

A subject is free to withdraw from the study at any time. In addition, a subject will be withdrawn if any of the following criteria are met:

- change in compliance with any inclusion/exclusion criterion that is clinically relevant and affects subject safety as determined by the Investigator (or designee).
- noncompliance with the study restrictions that might affect subject safety or study assessments/objectives, as considered applicable by the Investigator (or designee).
- any clinically relevant sign or symptom that, in the opinion of the Investigator (or designee), warrants subject withdrawal.

In the event of confirmed results for any of the following criteria, dosing of a subject with the IMP will be stopped permanently:

- QTcF increases > 60 msec compared to baseline (predose) and/or absolute QTcF values > 500 msec (confirmed by repeat measurement).
- Systemic exposure for any individual subject is predicted to exceed a C_{max} of 19755 ng/mL and/or an AUC_{0-24} of 52486 ng.h/mL; ie, systemic exposure will be no greater than the lowest exposure at the NOAEL.
- Liver chemistry results:
 1. ALT or AST > 5 x ULN, which is confirmed by repeat
 2. ALT or AST > 3 x ULN, which is confirmed and total bilirubin > 2 x ULN or international normalised ratio >1.5
 3. ALT or AST > 3 x ULN, which is confirmed and the new appearance (ie, onset coincides with the changes in hepatic enzymes) of fatigue, nausea, vomiting, right upper quadrant pain or tenderness, fever, rash,

or eosinophilia (> ULN) felt by the Investigator to be potentially related to hepatic inflammation/injury.

If a subject is withdrawn, the Sponsor will be notified and the date and reason(s) for the withdrawal will be documented in the subject's electronic Case Report Form (eCRF). If a subject is withdrawn, efforts will be made to perform all follow-up assessments, if possible ([Appendix 6](#)). Other procedures may be performed at the Investigator's (or designee's) and/or Sponsor's discretion. If the subject is in-house, these procedures should be performed before the subject is discharged from the clinic. The Investigator (or designee) may also request that the subject return for an additional Follow-up visit. All withdrawn subjects will be followed until resolution of all their AEs or until the unresolved AEs are judged by the Investigator (or designee) to have stabilised.

Subjects who are withdrawn for reasons not related to study drug may be replaced following discussion between the Investigator and the Sponsor. Subjects withdrawn as a result of AEs thought to be related to the study drug will generally not be replaced.

4.9. Study Termination

The study may be discontinued at the discretion of the Investigator (or designee), Sponsor, or Sponsor's Medical Monitor if any of the following criteria are met:

- adverse events unknown to date (ie, not previously reported in any similar investigational study drug trial with respect to their nature, severity, and/or duration).
- increased frequency, severity, and/or duration of known, anticipated, or previously reported AEs (this may also apply to AEs defined at Check-in as baseline signs and symptoms).
- medical or ethical reasons affecting the continued performance of the study.
- difficulties in the recruitment of subjects.
- cancellation of drug development.

5. STUDY TREATMENTS

5.1. Description, Storage, Packaging, and Labelling

The IMPs (5 and 50 mg GB1211 and placebo capsules) will be supplied by the Sponsor (or designee), along with the batch/lot numbers and Certificates of Analysis. A Certificate of Release authorised by a Qualified Person in the EU will also be issued for the IMP.

The IMP will be provided in high-density polyethylene bottles and stored according to the instructions on the label. The IMPs will be stored at the study site in a location that is locked with restricted access.

The bulk drug container and unit dose containers will be labelled in accordance with national laws and regulations. The IMPs will be transferred from bulk supplies into the subject's dose container by qualified clinical staff.

Capsules for the planned dose levels in Part A of the study will be assembled as shown in [Table 4](#).

Table 4: Capsule Assembly for Part A

Cohort	Dose Level (mg)	Number of Capsules to be Assembled	
		Dose of GB1211	Placebo
A1	5	1 x 5 mg	1 x capsules
A2	20	4 x 5 mg	4 x capsules
A3	50	1 x 50 mg	1 x capsules
A4	100	2 x 50 mg	2 x capsules
A5	200	4 x 50 mg	4 x capsules

